4.1 Inclusion criteria

Population eligible for inclusion in this study must fulfill all of the following criteria:

- 1. Written informed consent must be obtained before any assessment is performed
- 2. Able to communicate well with the investigator, to understand and comply with the requirements of the study.
- 3. Male and female adult patients aged ≥ 18 to ≤ 75 years.
- 4. Patients must weigh between 50 and 120 kg

- Amended Protocol Version v02 (Clean)
- 5. Patients with a physician-diagnosed history of moderate to severe asthma for a period of at least one year prior to screening
- 6. Patients on a stable therapy regimen for asthma for at least 3 months prior to screening with at least medium dose inhaled glucocorticoid and at least one additional asthma control medication (such as inhaled long-acting bronchodilator, leukotriene antagonist, theophylline, stable low dose glucocorticoid, etc)
- 7. Acceptable and reproducible spirometry with FEV1 > 40 and < 90 % of predicted at screening and baseline visits (Re-testing is allowed once)
- 8. ACQ score ≥ 1.5 at screening and baseline visits (Re-testing is allowed once)
- 9. Total serum IgE < 150 IU/mL at screening and baseline visits (Re-testing is allowed once)
- 10. Peripheral blood eosinophils < 300/μL at screening and baseline visits (Re-testing is allowed once)

4.2 **Exclusion criteria**

Population fulfilling any of the following criteria are not eligible for inclusion in this study:

- 1. Use of investigational drugs at the time of screening, or within 4 weeks or 5 half-lives of screening, or as required by local regulations, whichever is longer.
- 2. Treatment with IL-17 or IL-17R blocking agents over the previous 12 months, including, but not limited to secukinumab, ixekizumab, bimekizumab and brodalumab.
- 3. Previous use of biologics or other concomitant medications within time periods specified in the SOM/protocol.
- 4. Women of child-bearing potential, defined as all women physiologically capable of becoming pregnant, unless they are using highly effective methods of contraception during dosing and for 13 weeks after stopping of investigational drug. Highly effective contraception methods include:
 - Total abstinence from heterosexual intercourse (when this is in line with the preferred and usual lifestyle of the subject). Periodic abstinence (e.g. calendar, ovulation, symptothermal, post-ovulation methods) and withdrawal are not acceptable methods of contraception.
 - Female sterilization (have had surgical bilateral oophorectomy with or without hysterectomy), total hysterectomy or tubal ligation at least six weeks before taking investigational drug. In case of oophorectomy alone, only when the reproductive status of the woman has been confirmed by follow up hormone level assessment.
 - Male sterilization (at least 6 months prior to screening). For female subjects in the study the vasectomized male partner should be the sole partner for that subject.
 - Use of oral, injected or implanted hormonal methods of contraception or placement of an intrauterine device (IUD) or intrauterine system (IUS) or other forms of hormonal contraception that have comparable efficacy (failure rate <1%), for example hormone vaginal ring or transdermal hormone contraception

In case of use of oral contraception, women should be stable on the same pill for a minimum of 3 months before taking investigational drug.

Women are considered post-menopausal and not of child bearing potential if they have had 12 months of natural (spontaneous) amenorrhea with an appropriate clinical profile (e.g. age appropriate, history of vasomotor symptoms) or have had surgical bilateral oophorectomy (with or without hysterectomy), total hysterectomy or tubal ligation at least

oophorectomy (with or without hysterectomy), total hysterectomy or tubal ligation at least six weeks ago. In the case of oophorectomy alone, only when the reproductive status of the woman has been confirmed by follow up hormone level assessment is she considered not of child bearing potential.

- 5. Pregnant or nursing (lactating) women, where pregnancy is defined as the state of a female after conception and until the termination of gestation, confirmed by a positive hCG laboratory test.
- 6. History of ongoing, chronic or recurrent moderate or severe infectious disease.
- 7. Patients with chronic lung diseases other than asthma, including (but not limited to) chronic obstructive pulmonary disease, clinically significant bronchiectasis, sarcoidosis, interstitial lung disease, cystic fibrosis, Churg-Strauss syndrome, allergic bronchopulmonary aspergillosis, or clinically significant chronic lung diseases related to a history of tuberculosis or asbestosis.
- 8. History of severe systemic Candida infections or evidence of Candidiasis in the 2 weeks prior to baseline visit.
- 9. Active systemic infections during the 2 weeks prior to baseline.
- 10. History of immunodeficiency diseases, including a positive HIV (ELISA and Western blot) test result at screening.
- 11. A positive Hepatitis B surface antigen or Hepatitis C test result at screening
- 12. Any live vaccines (this includes nasal-spray flu vaccine) starting from 6 weeks before baseline
- 13. Any severe, progressive or uncontrolled, acute or chronic, medical or psychiatric condition, or other factors such as abnormal vital signs, ECG or physical findings, or clinically relevant abnormal laboratory values, that in the judgment of the investigator may increase the risk associated with study participation/treatment or may interfere with interpretation of study results, and thus would make the patient inappropriate for entry into or continuing the study.
- 14. History of hypersensitivity or allergy to the investigational compound/compound class being used in this study.
- 15. Donation or loss of 400 ml or more of blood within 8 weeks prior to baseline, or longer if required by local regulation.
- 16. History of drug or alcohol abuse within the 12 months prior to dosing.
- 17. At screening, history or symptoms of malignancy of any organ system (except for a history of basal cell carcinoma and/or up to 3 squamous cell carcinomas of the skin, if successful treatment has been performed, with no signs of recurrence; actinic keratosis, if present at screening, should be treated according to standard therapy before randomization), treated or untreated, within the past 5 years, regardless of whether there is evidence of local recurrence or metastases.
- 18. Patients with known active Crohn's disease.

- 19. Patients who have smoked or inhaled recreational foreign substances such as nicotine. tobacco products, marijuana, e-cigarettes, etc within the 6 month period prior to Visit 1, or who have any smoking history of greater than 10 pack years (e.g. 10 pack years = 1 pack/day x 10 years or ½ pack/day x 20 years, etc.) (Assume 1 pack = 20 cigarettes or equivalent).
- 20. History of life-threatening asthma event in the previous year, such as significant hypercarbia (pCO₂ > 45 mmHg), endotracheal intubation, non-invasive positive pressure ventilation (NIPPV), respiratory arrest, or seizure as a result of asthma.
- 21. Patients who have had an asthma attack/exacerbation requiring systemic corticosteroids for at least 3 continuous days within 4 weeks prior to screening (re-screening is permitted).
- 22. Patients who have had a respiratory tract infection or asthma worsening within 4 weeks prior to Visit 1 (Screening) or during the screening period. Patients may be re-screened 4 weeks after recovery from their respiratory tract infection or asthma worsening.

No additional exclusions may be applied by the investigator, in order to ensure that the study population will be representative of all eligible patients.

Restrictions for Study Subjects 5

During recruitment, screening/informed consent review, and baseline visit, the subjects must be informed and reminded of the restrictions outlined in this section.

5.1 **Contraception requirements**

Please refer to exclusion criteria (Section 4.2) for details of contraception requirements for the study.

Women of child bearing potential must be informed that taking the study treatment may involve unknown risks to the fetus if pregnancy were to occur during the study, and agree that in order to participate in the study they must adhere to the contraception requirement for the duration of the study. If there is any question that the subject will not reliably comply, they should not be entered or continue in the study.

Male subjects are not required to wear a condom for the duration of the study. However, he should be informed that if a female partner becomes pregnant while he is enrolled in the study, contact with the female partner will be attempted to request her consent to collect pregnancy outcome information.

5.2 **Prohibited treatment**

Each concomitant drug must be individually assessed against all exclusion criteria and the table below to see if it is allowed. If in doubt, the investigator should contact the medical monitor before randomizing a patient or allowing a new medication to be started. The following drugs are excluded to ensure patient safety and prevent confounding of efficacy in this clinical trial.

Table 5-1 Prohibited medication

Medication	Prohibited period	Action to be taken
IL-17 or IL17R blocking agents, including, but not limited to secukinumab, ixekizumab, bimekizumab and brodalumab.	12 months prior to screening through end of study	Exclude until patient re-qualifies for study
Anti-IgE biologic therapy such as omalizumab	3 months prior to screening through end of study	Exclude until patient re-qualifies for study
Anti-IL 4, 5 or 13 biologic therapy such as mepolizumab or dupilumab	3 months prior to screening through end of study	Exclude until patient re-qualifies for study
Other investigational drugs	4 weeks or 5 half-lives, whichever is longer	Exclude until patient re-qualifies for study
Live vaccine	6 weeks prior to baseline visit through end of study	Exclude until patient re-qualifies for study

5.3 Dietary restrictions and smoking

Study participants must refrain from smoking or inhaling nicotine or tobacco products or other recreational inhaled foreign substances such as marijuana, e-cigarettes, etc for the duration of the study.

Participants should refrain from alcohol and caffeine intake 24 hours and 8 hours prior to each study visit respectively.

5.4 Other restrictions

Study participants are expected to refrain from strenuous physical exercise (e.g. weight training, aerobics, football) until after Study Completion evaluation. Restrictions on bronchodilators are described in Section 6.10 and Section 6.11 of the protocol.

6 Treatment

6.1 Study treatment

Details on the requirements for storage and management of study treatment, and instructions to be followed for subject numbering, prescribing/dispensing and taking study treatment are outlined in the Site Operations Manual. Refer to Section 5.3 for 'Dietary restrictions and smoking' during study treatment.

6.1.1 Investigational treatment and control drugs

Table 6-1 Overview of study medication

Study drug name	Formulation Unit dose Packaging		Packaging	Provided by	
CJM112 150mg/1mL	Liquid in vial	150 mg/mL	Double Blind patient specific kits	Novartis	
Placebo to CJM112	Liquid in vial	0 mg/mL	Double Blind patient specific kits	Novartis	

6.1.2 Additional study treatment

No additional treatment beyond investigational drug and placebo are included in this trial. The study participant or the investigational site are responsible for sourcing all other treatments such as standard of care inhalers, rescue inhalers, etc.

6.2 Treatment arms

Company Confidential Information

6.3 Treatment assignment and randomization

At the Day 1 visit, all eligible patients will be randomized and treatment will be assigned via Interactive Response Technology (IRT). Randomization will be stratified by region (US, EU, and Rest of World). Standard of care practice for management of asthma may vary by region due to availability of inhalers; thus, we will stratify randomization by region. The IRT can be contacted via the interactive web response system (IWRS). The investigator or his/her delegate will contact the IRT after confirming that the subject fulfills all the inclusion/exclusion criteria.

The randomization numbers will be generated using the following procedure to ensure that treatment assignment is unbiased and concealed from subjects and investigator staff. A subject randomization list will be produced by the IRT provider using a validated system that automates the random assignment of subject numbers to randomization numbers. These randomization numbers are linked to the different treatment arms, which in turn are linked to medication numbers. A separate medication list will be produced by or under the responsibility of Novartis Drug Supply Management using a validated system that automates the random assignment of medication numbers to packs containing the investigational drug(s).

The randomization scheme for subjects will be reviewed and approved by a member of the Randomization Office.

Follow the details outlined in the Site Operations Manual regarding the process and timing of treatment assignment and randomization of subjects.

6.4 Treatment blinding

This is a subject and investigator-blinded study. Subjects and investigators will remain blinded to study treatment throughout the study, except where indicated below.

The identity of the treatments will be concealed by the use of study drugs that are all identical in packaging, labeling, schedule of administration, appearance, and odor.

Site staff

All site staff (including study investigator and study nurse) will be blinded to study treatment throughout the study.

Unblinding a single subject at site for safety reasons (necessary for subject management) will occur via an emergency system in place at the site (see Section 6.7).

Sponsor staff

The sample analysts will receive a copy of the randomization schedule (via request to the Randomization Office), to facilitate analysis of the samples. The sample analysts will provide the sample data to the study team under blinded conditions unless otherwise allowed.

The study statistician will be able to access the randomization list for interim analyses and is allowed to share unblinded information with the rest of the clinical team as appropriate for internal decision purposes, as outlined in Table 6-2. For example, unblinded summaries and unblinded individual data can be shared with the team for interim analyses.

Study programmers and other personnel involved in study data analysis (e.g. biomarker expert) are allowed to access treatment assignment information for the purpose of conducting interim analyses.

The clinical trial team is allowed to share unblinded results with other sponsor staff (e.g. decision boards) as required for internal decision making on the study or the project at the time of interim analyses while the study is ongoing.

All unblinded personnel will otherwise keep randomization lists and data or information that could unblind other study team members confidential and secure except as described above.

Following final database lock all roles may be considered unblinded.

Table 6-2 Blinding levels

	Time or Event				
Role	Randomization list generated	Treatment allocation & dosing	Safety event (single subject unblinded)	Interim Analysis	
Subjects/Patients	В	В	UI	В	
Site staff	В	В	UI	В	
Unblinded site staff (see text for details)	В	UI	UI	UI	
Drug Supply and Randomization Office	UI	UI	UI	UI	
Unblinded sponsor staff (see text for details)	В	UI	UI	UI	
Statistician/statistical programmer/data analysts	В	В	UI	UI	
Biomarker expert and data manager	В	В	UI	UI	
All other sponsor staff not identified above	В	В	UI	UI	

B Remains blinded

UI Allowed to be unblinded on individual patient level

6.5 Treating the subject

CJM112 150mg/1mL or placebo will be administered to the subject via the subcutaneous (s.c.) route of administration at the study site. See the Site Operations Manual for further details.

Sponsor qualified medical personnel will be readily available to advise on trial related medical questions or problems.

6.6 Permitted dose adjustments and interruptions of study treatment

Study treatment dose adjustments and/or interruptions are not permitted unless they are absolutely necessary for subject's safety. Any dose adjustments and/or interruptions will be recorded as protocol deviations. All changes must be recorded on the Dosage Administration Record CRF.

6.7 Emergency breaking of assigned treatment code

Emergency code breaks must only be undertaken when it is required to in order to treat the subject safely. Most often, study treatment discontinuation and knowledge of the possible treatment assignments are sufficient to treat a study subject who presents with an emergency condition. Emergency treatment code breaks are performed using the IRT. When the investigator contacts the system to break a treatment code for a subject, he/she must provide the requested subject identifying information and confirm the necessity to break the treatment code for the subject. The investigator will then receive details of the investigational drug treatment for the specified subject and a fax or email confirming this information. The system will automatically inform the study monitor for the site and the Study Team that the code has been broken.

It is the investigator's responsibility to ensure that there is a dependable procedure in place to allow access to the IRT system at any time in case of emergency. The investigator will need to provide:

- protocol number
- study drug name (if available)
- subject number.

In addition, the investigator must provide oral and written information to inform the subject how to contact his/her backup in cases of emergency when he/she is unavailable to ensure that un-blinding can be performed at any time.

An assessment will be done by the appropriate site personnel and sponsor after an emergency unblinding to assess whether or not study treatment should be discontinued for a given subject.

6.8 Treatment exposure and compliance

6.9 Recommended treatment of adverse events

AEs should be treated per the judgement of the responsible physician. Medication used to treat AEs must be recorded on the Concomitant medications/Significant non-drug therapies CRF.

6.10 Rescue medication

Use of short-acting rescue inhalers/bronchodilators for asthma, such as albuterol/salbutamol, is permitted. They must be sourced by the investigational site or the subjects themselves. Both short and long acting bronchodilators must be withheld prior to the study visits as described in the SOM. No other specific rescue treatments are planned for this study. Use of rescue medication must be recorded on the Concomitant medications/Significant non-drug therapies CRF.

6.11 Concomitant treatment

The investigator must instruct the subject to notify the study site about any new medications he/she takes after the subject was enrolled into the study.

All prescription medications, over-the-counter drugs and significant non-drug therapies (including physical therapy and blood transfusions) administered or taken within the timeframe defined in the entry criteria prior to the start of the study and during the study, must be recorded on the Concomitant medications/Significant non-drug therapies CRF.

Medication entries should be specific to trade name, the single dose and unit, the frequency and route of administration, the start and discontinuation date and the reason for therapy.

Each concomitant drug must be individually assessed against all exclusion criteria/prohibited medication. If in doubt, the investigator should contact Novartis before randomizing a subject or, if the subject is already enrolled, to determine if the subject should continue participation in the study.

7 Study completion and discontinuation

7.1 Study completion and post-study treatment

Each subject will be required to complete the study in its entirety, and thereafter no further study treatment will be made available to them.

Study completion is defined as when the last subject completes their End of Study visit and any repeat assessments associated with this visit have been documented and followed-up appropriately by the Investigator, or in the event of an early study termination decision, the date of that decision.

All subjects should complete the follow up visits 201, 202 and an End of Study visit 299. Additionally, in case the treatment is prematurely interrupted due to AE or any other reason and not resumed, site should conduct visit 201 approximately 7 days after the last treatment visit, visit 202 approximately 6 weeks after visit 201, and visit 299 approximately 6 weeks after visit 202. Thus, the patient will complete all 3 follow up visits, which will enable patient safety assessment for 13 weeks after the last dose. Additional unscheduled safety visits may be conducted per the judgement of the PI if required to ensure patient safety.

All SAEs reported during the entire study duration must be reported as described in Section 9.2 and the Site Operations Manual. If a subject is lost to follow-up, documentation of attempts to contact the subject should be recorded in the source documentation. Subjects are expected to continue their standard of care treatment during and after the study.

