3.1 Study design

This is a non-confirmatory, randomized, subject- and investigator-blinded, placebo-controlled, multi-center, parallel-arm study evaluating the efficacy of CJM112 on top of standard of care in patients with inadequately controlled moderate to severe asthma. This study will enroll approximately 110 patients. After an initial screening visit and run-in period of approximately 4 weeks, subjects eligible per inclusion and exclusion criteria at the baseline visit will be randomized (3:2) to receive Company Confidential Information CJM112 or matching placebo subcutaneously over 3 months during visits at the clinical study site. All baseline safety evaluation results must be available prior to the first dose. After the end of the treatment period, subjects will be followed for an additional 13 weeks. Site visits to administer dose and assess safety and efficacy will be scheduled as depicted in the figure below.

Figure 3-1 Study Design

Company Confidential Information

Screening and Run-In: Patients will provide informed consent and participate in an initial screening visit consisting of vital signs, physical exam, blood chemistry, ECG, pulmonary function tests, and ACQ. Subjects who meet all eligibility criteria at the screening visit will be dispensed a daily symptom diary and be asked to perform peak flow measurements over the approximately 4 week run-in period until the baseline visit.

Baseline: Subjects who qualify based on screening and run-in assessments will return for a baseline evaluation between Day -5 to Day -2. Subjects who meet all the applicable inclusion/exclusion criteria at screening and baseline will be randomized and will enter the treatment period. All screening and baseline assessments results must be available prior to randomization.

Treatment Period:

Company Confidential Information

At treatment period visits, safety, Company Confidential Information assessments will be performed. Safety assessments will include physical examinations, open ended health inquiry, ECGs, vital signs, standard clinical laboratory evaluations (hematology, blood chemistry, urinalysis), AEs and SAE monitoring.

Company Confidential Information

Company

Safety Follow-up: After completing the last dose Confidential Information, subjects will enter an additional follow-up period consisting of a visit on Day 92, Day 134 and an End of Study (EOS) visit on Day 176.

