Subjects who discontinue treatment early (unless they have withdrawn consent) should complete the D92, D134 and End of Study visit D176. All subjects who discontinue the study early (including subjects who withdraw consent) will be required to complete the EOS visit.

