If discontinuation of study treatment occurs, investigator must determine the primary reason for the subject's premature discontinuation of study treatment and record this information on the Dosage Administration CRF.

Subjects who discontinue study treatment or who decide they do not wish to participate in the study further should NOT be considered withdrawn from the study UNLESS they withdraw their consent (see Section 7.3, Withdraw of Informed Consent). Where possible, they should return for visits 201, 202 and 299. If they fail to return for these visits for unknown reasons, every efforts (e.g. telephone, e-mail, letter) should be made to contact the subject/predesignated contact as specified in Section 7.4 (Lost to follow-up).

The investigator must also contact the IRT to register the patient's discontinuation from study treatment.

After study treatment discontinuation, at a minimum, in abbreviated visits, the following data should be collected at clinic visits or via telephone/email contact:

- new / concomitant treatments
- adverse events/Serious Adverse Events

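### Protocol Sections 3.1 and 7.1 time the follow-up visits of patients who stop treatment early by different clocks, 14 to 84 days apart

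*Protocol*

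**What the plan says.** Protocol Section 3.1 describes the safety follow-up after the last dose as "consisting of a visit on Day 92, Day 134 and an End of Study (EOS) visit on Day 176". It then says that subjects who discontinue treatment early, unless they have withdrawn consent, "should complete the D92, D134 and End of Study visit D176".

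Section 7.1 uses visit numbers: "All subjects should complete the follow up visits 201, 202 and an End of Study visit 299". For early stoppers it has a separate timing rule, which begins "in case the treatment is prematurely interrupted due to AE or any other reason and not resumed, site should conduct visit 201 approximately". The rule sets an interval of about 7 days from the last treatment visit to visit 201, then about 6 weeks to visit 202, then about 6 weeks more to visit 299. The stated purpose is a schedule "which will enable patient safety assessment for 13 weeks after the last dose".

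Section 7.2 says of patients who discontinue: "Where possible, they should return for visits 201, 202 and 299". It gives no timing.

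**The concern.** Sections 3.1 and 7.1 each instruct sites on the same patients, one by study day and the other by time since the last treatment visit. Sites following different sections would hold the same numbered visit on different study days. Four things depend on those dates:

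- **Spirometry.** SAP Section 6.2 places pre- and post-bronchodilator spirometry at visits 201 and 299, among others. An early stopper's visit 201 would fall between about Day 8 and Day 78 under Section 7.1, and on Day 92 under Section 3.1.
- **Adverse event period.** Protocol Section 9.1 defines adverse events up to the end of study visit. A new event between the Section 7.1 date and Day 176 is inside the definition under one rule and outside it under the other.
- **Lost to follow-up.** Section 7.4 allows this status only once the scheduled end of study visit would have taken place. That date has two values.
- **Exacerbation analysis.** SAP Section 7.2 censors event-free completers at their End of Study visit in the time-to-first-exacerbation analysis. For event-free early stoppers who stay in the study, the length of follow-up depends on which rule the site used.

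No effect on the primary efficacy analysis is claimed, because the model and the assessment schedule are redacted.

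**Working it through.** **Inputs**

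- Dosing: five weekly doses, then four doses at two-week intervals (Protocol Section 3.3), with the last on Day 85 (Section 3.2). Dose days are therefore 1, 8, 15, 22, 29, 43, 57, 71 and 85.
- Fixed rule: Days 92, 134 and 176 (Section 3.1).
- Relative rule: +7 days, then +42, then +42 (Section 7.1).
- Assumption: the last treatment visit is the day of the last dose, *d*. This fits Section 7.1, which counts its intervals as time after the last dose.
- Inference: visits 201, 202 and 299 are the Day 92, 134 and 176 visits. Visit 299 is named as End of Study, and the days match exactly for a full course.

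**The plan's own figure.** 7 + 42 + 42 = 91 days = 13 weeks, as Section 7.1 states. For a full course, 85 + 7 = 92, 85 + 49 = 134 and 85 + 91 = 176, so the two rules coincide.

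**Early stoppers.** The relative rule gives *d* + 7, *d* + 49 and *d* + 91. The gap to the fixed rule is 92 − (*d* + 7) = 85 − *d*, and it is the same at all three visits. Under the fixed rule, the first follow-up visit comes 92 − *d* days after the last dose and End of Study comes 176 − *d* days after it. Under the relative rule these are about 7 and 91 days.

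| Last dose (Day *d*) | 201/202/299 under Section 7.1 (Day) | Gap to Days 92/134/176 (days) | Last dose to first visit, Section 3.1 (days) | Last dose to End of Study, Section 3.1 (days) |
|---|---|---|---|---|
| 1 | 8 / 50 / 92 | 84 | 91 | 175 |
| 8 | 15 / 57 / 99 | 77 | 84 | 168 |
| 15 | 22 / 64 / 106 | 70 | 77 | 161 |
| 22 | 29 / 71 / 113 | 63 | 70 | 154 |
| 29 | 36 / 78 / 120 | 56 | 63 | 147 |
| 43 | 50 / 92 / 134 | 42 | 49 | 133 |
| 57 | 64 / 106 / 148 | 28 | 35 | 119 |
| 71 | 78 / 120 / 162 | 14 | 21 | 105 |
| 85 (full course) | 92 / 134 / 176 | 0 | 7 | 91 |

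**Adverse event period.** The days covered under Section 3.1 but not under Section 7.1 run from Day *d* + 92 to Day 176, which is 85 − *d* days. For *d* = 1 this is Days 93 to 176 (84 days); for *d* = 71 it is Days 163 to 176 (14 days).

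**The case against.** The best counter-reading is that D92, D134 and D176 in Section 3.1 are only names for visits 201, 202 and 299. The next sentence of Section 3.1 gives this some support. It asks patients who leave the study, including those who withdraw consent, to complete the End of Study visit, and Section 7.3 puts their final evaluation at the time of withdrawal. For them, End of Study cannot mean Day 176. Section 7.1 is also the only text that gives explicit intervals after an early stop, and a note in the unseen assessment schedule, study design figure or Site Operations Manual might settle the matter.

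This does not remove the conflict. The sentence about leaving the study covers a different group and attaches no day to the visit. The sentence about stopping treatment attaches the day numbers to the very patients for whom label and date diverge, and Section 3.1 has just presented those numbers as study days. Nor can "approximately" in Section 7.1 absorb a gap of 2 to 12 weeks. A note elsewhere would still leave the two body sections in disagreement.

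The safety consequence is softened, and that part of the objection stands:

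- Section 7.2 requires that "at a minimum, in abbreviated visits, the following data should be collected at clinic visits or via telephone/email contact", covering new treatments and adverse events.
- Section 7.1 allows for extra contact: "Additional unscheduled safety visits may be conducted per the judgement of the PI if required to ensure patient safety".
- Section 9.1 has detected events followed to resolution, and later events thought to be related reported by the patient.
- Section 9.2.2 requires all serious events to be reported until 30 days after the end of the study. Even counted from the patient's own Section 7.1 End of Study date, this passes Day 176 for last doses on Day 57 (148 + 30 = 178) and Day 71 (162 + 30 = 192).

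For patients who have an asthma exacerbation adverse event, SAP Section 4 excludes later efficacy assessments from the PD analysis set whichever day they fall on, so visit timing does not matter for that set. None of these provisions fixes when the visits occur.

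**Conclusion.** The contradiction is real. For every last-dose day before Day 85, the two sections place all three follow-up visits 14 to 84 days apart. End of Study falls between about Day 92 and Day 162 under Section 7.1, and on Day 176 under Section 3.1.

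This rests on taking the last treatment visit as the last-dose day and on the inferred match between visit numbers and study days. The Section 7.1 dates are approximate by its own wording. The 84-day gap needs a stop after a single dose, and without an early-stopping rate the number of patients affected cannot be given. The point should be corrected because it changes what sites do and which data are counted, but its effect is confined to early stoppers and eased by the safeguards above.

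**What to change.** Reconcile Protocol Sections 3.1, 7.1 and 7.2 on a single timing rule for the follow-up visits of patients who stop treatment early. The choice is the sponsor's; none is proposed here and no extra visit is requested. Then confirm that the following match the chosen rule:

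1. the end of the adverse event period (Protocol Section 9.1);
2. the lost-to-follow-up date (Protocol Section 7.4);
3. the analysis visit to which early stoppers' follow-up spirometry is assigned;
4. End of Study censoring in the time-to-first-exacerbation analysis (SAP Section 7.2).

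The cost is a wording amendment to the protocol, with its administrative work, and a check of the existing analysis derivations.
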